14. LIST OF APPENDICES

| APPENDIX I | Statistical Plan | |
|------------|------------------|--|

Appendix 1 Statistical Plan

Objective

The primary objective of the trial is to verify that the Prismaflex HF20 Set is able to deliver effective treatment in small patients. Its efficacy will be measured by the reduction in blood urea nitrogen (BUN). This will be measured every 12 hours at the start of, and during, treatment. Creatinine reduction and the TCO₂ profile will be assessed as secondary endpoints along with survival time of the Prismaflex HF20 Set out to 72 hours.

. A repeated measures ANOVA will be used to test TCO₂. No formal statistical analysis of the safety endpoint will be carried out; rather these events will be assessed for severity and device-relatedness, and reported in narrative form.

Primary Endpoint

The primary endpoint of analysis will be to demonstrate that a mean reduction of greater than 38% in BUN is seen at 24 hours from initiation of CRRT. This percentage reduction is motivated by the target of getting patients with an initial BUN of 80 mg/dL below 50 mg/dL after 24 hours of treatment.

The null hypothesis to be tested is

*H*₀:
$$\mu \le 38$$
, vs
*H*_a: $\mu > 38$

Where μ stands for the mean percentage reduction in BUN from baseline to 24 hours.

Secondary Endpoints

A secondary endpoint will consist of testing whether there is a significant change in creatinine and TCO_2 from baseline to 24 hours. This will be done by turning the creatinine and TCO_2 readings into percent change from baseline and testing whether the percent change is significantly different from zero for each parameter. Another secondary endpoint is the survival time of the Prismaflex HF20 Set. The failure time of the Prismaflex HF20 Set, defined as when one of the following two alarms continues to

be triggered despite mitigation steps, "Warning: Filter Clotted", and/ or "Caution: TMP Excessive", will be recorded and analyzed to determine the survival function of the filter set. Safety will also be investigated by reporting: AEs, SAEs, device deficiencies and alarms.

In addition, the mean concentrations of BUN, creatinine and TCO₂ will be computed, along with 95% confidence intervals, at baseline and at each subsequent 12-hour sampling time.

Other Measures

Other patient and treatment measures will be captured during each patient's treatment. Summary numbers for these measures (mean, standard deviation, minimum and maximum) will be reported for each time point at which the measure is made.

Statistical Analysis Plan

Analysis of Primary Endpoint

The primary endpoint for the reduction in BUN will be assessed using a one-sample t test.

The actual mean percentage reduction in BUN will be quantified using 95% confidence intervals.

As a supportive analysis, an analysis of variance (ANOVA) will be implemented to investigate the mean change from baseline among the different sites.

The Analysis of the primary endpoint will be carried out on both the FA and PP.

Analysis of Secondary Endpoints

The change from baseline in creatinine and TCO₂ will be analyzed as described above for the primary endpoint.

The survival time of the Prismaflex HF20 Set will be analyzed using a Kaplan Meier survival curve to generate the survival function of the filter set.

AEs, SAEs and Device Deficiencies will be summarized by seriousness, relationship to study device, severity and overall frequency. Fluid Flow Alarms will also be reported.

The secondary analysis will be carried out on the FA.

Exploratory Trend Analysis

Analysis Populations

Full Analysis Set (FA): The Full Analysis Set is based on the intent-to-treat principle and includes any patient who received CRRT on the Prismaflex HF 20 Set for any period of time.

Per-Protocol Analysis Set (PP): The Per-Protocol Analysis Set defines a subset of the FA including patients who

• fulfilled all inclusion criteria

- did not meet any of the exclusion criteria
- received at least 20 hours of CRRT treatment on the Prismaflex HF20 Set with no more than 1 interruption which may have included a filter change.
- did not have major protocol deviations that might impact the assessment of the primary endpoint
- have available measurements for the primary endpoint (BUN) at baseline (within 1 hour prior, and 15 min after initiation of CRRT) and at 24 hours (±1 hour) from start of CRRT

Dropout

The primary endpoint is assessed at 24 hours, with a baseline reading within one hour prior to CRRT initiation and within 15 minutes after start of CRRT, patients are allowed one interruption which may include a filter change lasting up to 4 hours. Patients with an interruption lasting more than 4 hours or with a second Prismaflex HF20 Set change will be excluded from the PP.

Sample Size

The sample size calculation is based on the primary objective of 24-hour BUN reduction. It is anticipated that the true mean reduction at 24 hours will be some 62%, as would be obtained from a patient with initial BUN of 80 mg/dL and reaching 30 mg/dL after 24 hours of treatment. Data from the earlier M-10 study suggest that the standard deviation in the BUN reduction is about 45%.

Under these assumptions, the sample size needed to obtain 80% power is 24, as reported by SAS PROC POWER.

A target sample size of up to 30 patients is therefore proposed to allow for a possible 20% loss of data between the baseline and 24 hour marks.

2. LIST OF ABBREVIATIONS AND DEFINITIONS OF TERMS

ACT Activated Clotting Time

ADE Adverse Device Event

AE Adverse Event

AKI Acute Kidney Injury

APTT Activated Partial Thromboplastin Time

ANOVA Analysis of Variance

B2M Beta 2 Microglobulin

BP Blood Pressure

BUN Blood Urea Nitrogen

CI Confidence Interval

Cr Creatinine

CRF Case Report Form

CRRT Continuous Renal Replacement Therapy

eCRF Electronic Case Report Form

FAS Full Analysis Set

FDA Food and Drug Administration

FUN Fluid Urea Nitrogen

g/dl Grams per Deciliter

GCP Good Clinical Practices

hr Hour

HGB Hemoglobin

HIPAA Health Information Portability and Accountability Act

ICU Intensive Care Unit

ITT Intent-to-treat

IRB Institutional Review Board

kg Kilograms

KDIGO Kidney Disease Improving Global Outcomes

L Liter

lbs Pounds

MAP Mean Arterial Pressure

MedDRA Medical Dictionary for Regulatory Activities

MCMC Markov Chain Monte Carlo

mg Milligram

min Minute

ml Milliliter

mmHg Millimeters of Mercury

PBP Pre-Blood Pump

PICU Pediatric Intensive Care Unit

PPS Per Protocol Set

PTT Partial Thromboplastin Time

SAE Serious Adverse Event

SAP Statistical Analysis Plan

SD Standard Deviation

SE Standard Error

time (may appear in multiple formats [e.g., t'] as it can designate different time

periods like "time since drug administration" or "time of infusion"

TCO2 total carbon dioxide: CO2 in physical solutions or loosely bound to proteins,

bicarbonate (HCO3) or carbonate (CO3) anions, and carbonic acid (H2CO3).

TMP Transmembrane Pressure

US United States

### 3. INTRODUCTION

The statistical analysis plan (SAP) is created based on study Protocol 1463 Amendment 6.1 dated 06 December 2017.

This SAP describes the patient populations that will be analyzed, the variables that will be used for the analyses and the statistical methods that will be employed, which, will be used to guide statistical programming. The intention of the SAP is to expand on the details of the planned statistical methods described in the study protocol.

### 4. TRIAL OBJECTIVES

This clinical evaluation will focus on using a new high-flux dialyzer, Prismaflex HF20 Set (Gambro Industries, France) and related support in the Prismaflex System Software Version 7.10 and 7.20 (Gambro Lundia AB, Sweden) for CRRT in children in centers with extensive experience in pediatric dialysis. 1,2 Software Version 7.10 and Version 7.20 of the Prismaflex have been developed to safely treat children weighing down to 8 kg with respect to fluid balance.

### 4.1 Primary Objectives

The primary objective of this study is to evaluate the efficacy of the Prismaflex HF20 Set based on testing the hypothesis that it delivers sufficient renal replacement therapy (>38% reduction of Blood Urea Nitrogen (BUN) from baseline to 24 hours) to effectively treat Acute Kidney Injury (AKI) in pediatric patients weighing  $\geq$ 8 and  $\leq$ 20 kg (ie,  $\geq$ 17.6 and  $\leq$ 44.09 lbs).

### 4.2 Secondary Objectives

The secondary objectives of this study are:

- To evaluate the efficacy of removing creatinine and normalizing bicarbonate.
- To evaluate the safety of the Prismaflex System Software Version 7.10 and 7.20 in pediatric AKI patients weighing  $\geq 8$  and  $\leq 20$  kg (ie,  $\geq 17.6$  and  $\leq 44.09$  lbs).
- To determine how long a duration of time each Prismaflex HF20 Set can be used up to a maximum of 72 hours from the initiation of CRRT.

### 4.3 Exploratory Objectives

### 5. STUDY DESIGN AND CONDUCT CONSIDERATIONS

### 5.1 Study Design

The clinical study design is a multicentric, open label, single group study in which patients meeting all the inclusion criteria and none of the exclusion criteria of the study protocol, and deemed treatable by their physician with the Prismaflex HF20 Set and Prismaflex System Software Version 7.10 or with the Prismaflex HF20 Set and Prismaflex System Software Version 7.20, will be enrolled in the study. Patients included in the analysis will be treated for a minimum period of 20 of the first 24 hours and up to 72 hours with each Prismaflex HF20 Set with BUN, creatinine and bicarbonate being measured for statistical analysis at 12 hour intervals during CRRT treatment.

The duration of time for which each Prismaflex HF20 Set can be used will be evaluated out to a time period of 72 hours from the initiation of CRRT in each patient. The end of the extracorporeal circuit life will be defined by the occurrence and failure to mitigate one or both of the following Prismaflex System alarms, after which CRRT will be terminated and the extracorporeal circuit replaced:

• "Warning: Filter Clotted", and/or

• "Caution: TMP Excessive"

At 72 hours from the initiation of HF20 study CRRT, if the patient has been on the current Prismaflex HF20 Set for less than 72 hours, the patient is allowed to continue on their current filter set until the end of filter life (please refer to the study Protocol Section 3.2 for explicit detail). The site may follow applicable institutional practices if additional CRRT is required.

### **5.1.1 Baseline Definition**

All baseline values will be collected during the study visit in which study CRRT treatment is initiated. Baseline measure for laboratory assessments is defined as within 1 hour prior to or within 15 minutes after the initiation of CRRT.

Baseline values for BUN will be utilized in the primary endpoint analysis while creatinine and bicarbonate baseline values will be utilized in the secondary endpoint analysis.

### 5.2 Sample Size

The sample size calculation is based on the primary objective of 24hours BUN reduction. It is anticipated that the true mean reduction at 24 hours will be some 62%, as would be obtained from a patient with initial BUN of 80 mg/dL and reaching 30 mg/dL after 24 hours of treatment. Data from the earlier M-10 study suggest that the standard deviation in the BUN reduction is about 45%.

Under these assumptions, the sample size needed to obtain 80% power is 24, as reported by SAS PROC POWER.

A target sample size of up to 30 patients is therefore proposed to allow for a possible 20% loss of data between the baseline and 24 hours mark.

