3.1 Study duration

The study is planned to start in November 2015 (First Visit, First Patient) and to stop in December 2018 (Last Patient, Last Visit). It may be terminated earlier if sufficient patient numbers (24) reach the primary endpoint of 24 hours of CRRT or later if 24 patients have not achieved the endpoint for analysis.

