### 7. STATISTICAL ANALYSIS

### 7.1 General/Types of Analyses

Unless otherwise noted, all analyses will be performed using SAS/GRAPH® 9.4 software, SAS/STAT® 14.1 software and Base SAS® 9.4 software. Copyright© SAS Institute Inc. SAS and all other SAS Institute Inc. product or service names are registered trademarks or trademarks of SAS Institute Inc., Cary, NC, USA. All Rights Reserved.

Unless otherwise specified, treatment effects will be evaluated on the basis of a 2-sided significance level of 0.050 (when rounded to three decimal places).

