### 12. EFFICACY PARAMETERS

### 12.1 Primary Analysis

The primary analysis will be to demonstrate a mean reduction of greater than 38% in BUN at 24 hours from initiation of CRRT. This percentage of reduction is motivated by

the target of getting patients with an initial BUN of 80 mg/dL below 50 mg/dL after 24 hours of treatment.

The hypothesis to be tested is:

$$H_0$$
:  $\mu \leq 38\%$ ,

$$H_a$$
:  $\mu > 38\%$ 

Where  $\mu$  stands for the mean percentage reduction in BUN from baseline to 24 hours calculated as:

$$\mu = \frac{BUN_{0hr} - BUN_{24hr}}{BUN_{0hr}} \times 100\%$$

Where BUNohr is BUN recorded at baseline and BUN24hr is BUN recorded at 24 hours after CRRT initiation.

This hypothesis will be tested using a one-sample t test and the actual mean percentage reduction in BUN will be quantified using a 95% confidence interval.

As a supportive analysis, an analysis of variance (ANOVA) will be implemented to investigate the mean change from baseline among the different sites.

A box plot will also be generated to represent the 24 hours change in BUN from baseline.

The primary analysis of the primary endpoint will be based on the FAS. As supportive analysis, the same analysis will be carried out on the PPS.

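### The 80% power claimed for 24 patients holds only for a one-sided 0.05 test; at the SAP's two-sided 0.05 level, 24 evaluable patients give about 71%

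*SAP*

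**What the plan says.** The sample-size paragraph is the same in SAP 5.2 and in Protocol Appendix 1. On the expected effect it says "It is anticipated that the true mean reduction at 24 hours will be some 62" percent. On variability it cites an earlier study as suggesting that "the standard deviation in the BUN reduction is about 45" percent. It then concludes: "Under these assumptions, the sample size needed to obtain 80% power is 24, as reported by SAS PROC POWER". Up to 30 patients are to be enrolled to allow for 20% loss of data by 24 hours. Neither paragraph gives an alpha or says whether the test is one-sided or two-sided.

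The level appears only in SAP 7.1: "Unless otherwise specified, treatment effects will be evaluated on the basis of a 2-sided significance level of 0.050".

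SAP 12.1 sets the aim of the primary analysis, which is to "demonstrate a mean reduction of greater than 38% in BUN at 24 hours from initiation of CRRT". It writes the hypotheses as μ ≤ 38% against μ > 38%, names a one-sample t test, and adds that "the actual mean percentage reduction in BUN will be quantified using a 95% confidence interval". It gives no alpha of its own. SAP section 11, which lists the changes from the protocol, does not mention alpha or sidedness.

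On stopping, Protocol 3.1 says of the study: "It may be terminated earlier if sufficient patient numbers (24) reach the primary endpoint of 24 hours of CRRT".

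**The concern.** The sample size and the significance level come from different tests. The number 24 matches a one-sided 0.05 calculation that is written nowhere, while the level that is written is two-sided. Two things follow.

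First, under its own stated level the design lacks its stated power. The chance of missing a true 62% reduction at 24 patients is about 29%, against the 20% that a reader would infer.

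Second, the rule for success is ambiguous. A primary result with a one-sided p-value between 0.025 and 0.05 succeeds on the basis used to size the study and fails under the SAP. It would also be reported beside a 95% confidence interval that includes 38%. SAP section 11 removes the creatinine and bicarbonate tests, so this is the only test against a stated efficacy target, in an open-label study done to support device clearance. The choice between the two readings should not be left until the data are visible.

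**Working it through.** **Inputs**

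- True mean reduction 62%, SD 45%, power 80%: SAP 5.2
- Null value 38%, one-sample t test, alternative μ > 38%: SAP 12.1
- Level two-sided 0.05 unless otherwise specified: SAP 7.1
- Planned loss 20%, enrolment up to 30: SAP 5.2
- Number at which the study may stop, 24: Protocol 3.1

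**Method.** Exact one-sample t-test power from the noncentral t distribution with n − 1 degrees of freedom. The standardised difference is (62 − 38)/45 = 24/45 = 0.533, and the noncentrality is 0.533 × √n (2.61 at n = 24). Power is the probability that the statistic exceeds the critical value: t(0.95, n − 1) for one-sided 0.05, and t(0.975, n − 1) for two-sided 0.05, where the opposite tail adds almost nothing.

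**Reproducing the plan's figure, then applying the SAP's level**

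| n evaluable | Power, one-sided 0.05 | Power, two-sided 0.05 |
|---|---|---|
| 23 | 79.8% | 68.6% |
| 24 | 81.3% | 70.6% |
| 29 | 87.6% | 79.2% |
| 30 | 88.6% | 80.6% |

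The smallest n with at least 80% power is 24 one-sided, which is the plan's figure exactly. It is 30 two-sided. A one-sided 0.025 test also gives 30.

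**Loss allowance.** 24/(1 − 0.20) = 30, which reproduces the enrolment target. To keep 80% power at two-sided 0.05 after the same loss, enrolment would have to be 30/(1 − 0.20) = 37.5, so 38.

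**Does rounding explain the gap?** The plan derives 62% from a fall from 80 to 30 mg/dL (62.5% unrounded) and 38% from a fall from 80 to 50 mg/dL (37.5% unrounded).

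| Mean against null | Difference | Two-sided power at 24 | Two-sided n for 80% |
|---|---|---|---|
| 62 against 38 | 24 | 70.6% | 30 |
| 62.5 against 38 | 24.5 | 72.4% | 29 |
| 62.5 against 37.5 | 25 | 74.1% | 28 |

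None reaches 80% at 24. With the difference at 24, the SD would have to be about 40.2, not 45.

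**Pass mark at n = 24 with an observed SD of 45.** The standard error is 45/√24 = 9.19.

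- One-sided 0.05: 1.714 × 9.19 = 15.7, so the observed mean must exceed 38 + 15.7 = 53.7%.
- Two-sided 0.05, equivalent to a lower 95% confidence limit above 38%: 2.069 × 9.19 = 19.0, so the observed mean must exceed 38 + 19.0 = 57.0%.

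Observed means between 53.7% and 57.0% pass one rule and fail the other.

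**The case against.** The strongest reply is that 24 is not a miscalculation. Both documents write a directional hypothesis, a one-sided 0.05 test is a natural reading of it, and that test gives 24 and then 30 exactly. SAP 7.1 is a general default with an exception clause, and the directional hypothesis in 12.1 might count as the exception. The Protocol itself states no two-sided level. The 95% interval is there to quantify the reduction and is not named as the decision rule. The 71% is also the low end: it assumes exactly 24 analysed patients, stopping at 24 is optional, and two-sided power rises to 74.3% at 26, 77.7% at 28 and 80.6% at 30. If the two-sided rule stands, the type I error is protected and only the stated power is optimistic.

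Part of this stands. The number was computed correctly for an unstated test, and the interval is not a declared success criterion. But a directional alternative does not fix alpha: μ > 38% can be tested at 0.05 or at 0.025, the upper tail of the level in SAP 7.1. No passage says one-sided 0.05, so the default governs the primary test as written. The last patients up to 30 cannot be counted on, because they are the allowance for the planned loss.

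**Conclusion.** The concern holds. Under the only significance level in the documents, 24 evaluable patients give 70.6% power, not 80%, and 30 evaluable patients are needed. Unrounded versions of the plan's own examples raise the figure at 24 only to 72–74%. Full power at two-sided 0.05 requires all 30 enrolled patients to be evaluable, with no loss.

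The power figures rest on the plan's mean and SD, approximately normal data, and reading SAP 7.1 as applying to the primary test. If the sponsor meant one-sided 0.05, the sample size is right and the defect is that the level was never stated. On either reading the success rule must be settled before analysis, because it decides whether the primary endpoint passes.

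**What to change.** State one alpha, one sidedness and one success rule in SAP 12.1, then bring SAP 5.2 and Protocol Appendix 1 into line. There are two ways to do it.

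1. **Keep two-sided 0.05 (preferred, because it is the level already written and it fits the 95% interval).** Success means a lower 95% confidence limit above 38%. Restate power as about 71% with 24 evaluable patients and about 81% if all 30 are evaluable.
2. **Declare one-sided 0.05.** Name it in 12.1 as an exception to 7.1, give the reason, add the alpha to 5.2, and report the matching one-sided 95% lower bound (the lower limit of a two-sided 90% interval). The figures of 24 and 80% then stand.

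Either is a change of wording and needs no extra patients. The cost of the first is a less favourable power statement: it discloses the shortfall but does not remove it. Restoring 80% power at two-sided 0.05 with the planned loss would take 38 enrolled, which is a change of design.

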### 5.3 Randomization Procedure

This study is not randomized as all patients will be treated with the Prismaflex HF20 Set and Prismaflex System Software Version 7.10 or Prismaflex HF20 Set and Prismaflex System Software Version 7.20.

### 5.4 Schedule of Visits and Procedures

The schedule of events is presented below in Table 1.

**Table 1 Schedule of Events** 

Assessment	Up to 24 Hours Prior to CRRT (Screening)	At Initiation of CRRT (**Baseline)	12 Hours	24 Hours	36 Hours	48 Hours	60 Hours	72 Hours	HF20 CRRT End (if between 12 hours intervals)
Inclusion	X								
Exclusion	X								
Informed Consent	X								
Demographics	X								
Vitals	X	Hourly (± 15 min)	Hourly (± 15 min)	X (± 15 min)					
TMP		Hourly (± 15 min)	Hourly (± 15 min)	Hourly (± 15 min)	Hourly (± 15 min)	Hourly (± 15 min)	Hourly (± 15 min)	Hourly (± 15 min)	X (± 15 min)
Record Periodic & Cumulative Patient Fluid Removal (from GUI display)		Hourly (± 15 min)	Hourly (± 15 min)	Hourly (± 15 min)	Hourly (± 15 min)	Hourly (± 15 min)	Hourly (± 15 min)	Hourly (± 15 min)	X (± 15 min)
Record Periodic Unintended Patient Fluid Loss/Gain (from GUI display)		Hourly (± 15 min)	Hourly (± 15 min)	Hourly (± 15 min)	Hourly (± 15 min)	Hourly (± 15 min)	Hourly (± 15 min)	Hourly (± 15 min)	X (± 15 min)
Medical & Surgical History	X								
Diagnosis	X								

Assessment	Up to 24 Hours Prior to CRRT (Screening)	At Initiation of CRRT (**Baseline)	12 Hours	24 Hours	36 Hours	48 Hours	60 Hours	72 Hours	HF20 CRRT End (if between 12 hours intervals)
General Labs	Up to 24 hr prior	(Within 1 hr prior to or within 15 min after start of CRRT	+/- 1 hr	+/- 1 hr	+/- 1 hr	+/- 1 hr	+/-1 hr	+/-1 hr	If after 24 hours, may use previous 12 hour labs if CRRT ends between 12 hours assessment intervals hour time point acceptable
BUN	X	X	X	X	X	X	X	X	
Bicarbonate	X	X	X	X	X	X	X	X	
Serum Sodium	X	X	X	X	X	X	X	X	
Creatinine	X	X	X	X	X	X	X	X	
Potassium	X	X	X	X	X	X	X	X	
Chloride	X	X	X	X	X	X	X	X	
Phosphorous	X	X	X	X	X	X	X	X	
Albumin	X	X	X	X	X	X	X	X	
Total Calcium	X	X	*	*	*	*	*	*	*
Beta 2 Microglobulin		X		X		X		X	
Hemoglobin	X	*	*	*	*	*	*	*	

Assessment	Up to 24 Hours Prior to CRRT (Screening)	At Initiation of CRRT (**Baseline)	12 Hours	24 Hours	36 Hours	48 Hours	60 Hours	72 Hours	HF20 CRRT End (if between 12 hours intervals)
Heparin Use Only Labs									
Clotting Parameters Labs (PTT, APTT, ACT)		*	*	*	*	*	*	*	*
Citrate Use Only Labs									
Extracorporeal Circuit Calcium		*	*	*	*	*	*	*	
Patient Ionized Calcium		*	*	*	*	*	*	*	
CRRT Treatment									
Treatment Prescription		X	X	X	X	X	X	X	
Priming Solutions		X	X	X	X	X	X	X	
Anticoagulation		X	X	X	X	X	X	X	
Dialysate		X	X	X	X	X	X	X	
CRRT Treatment Details		X	X	X	X	X	X	X	
Treatment Modality		X	X	X	X	X	X	X	
Record Bag Weights		*	*	*	*	*	*	*	*

Assessment	Up to 24 Hours Prior to CRRT (Screening)	At Initiation of CRRT (**Baseline)	12 Hours	24 Hours	36 Hours	48 Hours	60 Hours	72 Hours	HF20 CRRT End (if between 12 hours intervals)
Record Syringe Volume		X	X	X	X	X	X	X	X
Filter Changes		X	X	X	X	X	X	X	
Patient Weight	X	X		X		X		X	X
Fluid Overload Assessment 	X	X	X	X	X	X	X	X	X
Survival Status								X	X
Protocol Deviations		X	X	X	X	X	X	X	X
AE	X	X	X	X	X	X	X	X	X
SAE	X	X	X	X	X	X	X	X	X
Con Meds	X	X	X	X	X	X	X	X	X
Alarms		X	X	X	X	X	X	X	X
* As determined by of car		**Basel	ine labs are to l	be obtained wit	hin 1 hour prio	r to start of CRI	RT or within 15	minutes after sta	art of CRRT

<sup>1 Degree of fluid overload assessment = fluid intake(L)-fluid output (L)/ICU admission weight (kg) (×) 100%

